11.1 Demographic and other Baseline characteristics

Variables: Table 11-1 shows which variables to analyse for the different analysis data sets.

Analysis method: Demographic and BL characteristics will be analysed by means of descriptive statistics. The start of the Raxone[®] treatment will be used as the BL (LEROS ITT).

Table shell structure is presented section 19.2.

Table 11-1 - Demographic and BL characteristics by analysis sets and subgroups

				Analys	is sets		
	Variable Type ¹	LEROS mITT / NH matched sets ²	Safety population	LEROS ITT	mtDNA subgroups ³	Age at BL subgroups ³	Best VA at BL subgroups ³
Demographics					J		
Gender	N	Х	Х	Х	Х	х	Х
Child bearing potential	N	-	Х	х	х	х	Х
Mutation	N	х	Х	х	Х	х	Х
Race	N	-	Х	х	Х	х	Х
Height	С	-	х	х	Х	х	Х
Weight	С	-	х	х	Х	х	Х
Age at BL	С	х	х	х	Х	х	Х
Baseline characteristics			^				
Age at 1 st symptoms onset ⁴	С	х	-	х	Х	х	х
Months since 1 st symptoms onset	С	х	-	х	Х	х	х
Months since most recent symptoms onset	С	Х	-	х	х	х	х

Number of symptomatic eyes per patient	0	х	-	Х	х	х	х
Eye with 1 st symptoms onset	N	х	-	х	Х	х	х
Delta onset (months) ⁵	С	Х	-	Х	х	x	×

¹ Variable Type: nominal (N), ordinal (O), continuous (C); ² Matched data sets (as defined in section 8.5) used in the calculation of 12 and 24 months endpoints evaluation; ³ Subgroups are to be analysed as defined in 9.3; ⁴ Age calculated as date of baseline visit minus date of birth, divided by 365.25; ⁵ Patients whose eyes have the same date of symptom onset will not be accounted

Listings: LEROS Safety population race, gender, weigh, height, age at baseline and LHON mtDNA will be listed, order by patient unique identification number.

For Natural History patients gender, age at baseline and LHON mtDNA will be listed, order by report survey, center and patient identification.

11.2 Visual Acuity

VA at BL, follow-up (month 6, 12, 18 and 24) and at nadir (as defined in section 16) will be analysed by means of descriptive statistics.

VA variables to analyse for the different analysis data sets and subgroups are described in Table 11-2 to Table 11-4. Table shells structure is presented in section 19.2.

Listings:

LEROS Safety population date of visit, type of visit (baseline, follow-up month or unscheduled), left eye logMAR, left eye semi-quantitative, right eye logMAR and right eye semi-quantitative will be listed, order by center, patient identification and date of visit.

For Natural History patients date of visit, left eye logMAR, left eye semi-quantitative, right eye logMAR and right eye semi-quantitative will be listed, order by report survey, center, patient identification and date of visit.

11.2.1 Visual Acuity at BL

Baseline descriptive statistics will be presented both for eyes and patients. Variables to be analysed by Month 12 and 24 visits are presented in Table 11-2.

SNT-IV-005 Statistical Analysis Plan

Confidential

Table 11-2 – Visual Acuity at BL by analysis sets and subgroups

		Analysis sets						
VA at BL	Variable Type ¹	LEROS mITT / NH matched sets ³	LEROS ITT	mtDNA subgroups ³	Age at BL subgroups ³	Best VA at BL subgroups ³		
Based in total of Patients								
Best VA by blindness category	0	х	Х	Х	Х	х		
Best VA (logMAR)	С	Х	Х	Х	Х	х		
Based in total of Eyes								
Months since symptoms onset	С	Х	Х	Х	Х	х		
Eyes VA by blindness category	0	Х	Х	Х	Х	х		
Eyes VA (logMAR)	С	Х	Х	Х	Х	Х		

Variable Type: nominal (N), ordinal (O), continuous (C); Matched data sets (as defined in section 8.5) used in the calculation of 12 and 24 months endpoints evaluation; Subgroups are to be analysed as defined in 9.3;

11.2.2 Visual Acuity at Nadir

Nadir (as defined in section 16) descriptive statistics will only be presented for eyes. Variables to be analysed are presented in Table 11-3.

Time to Nadir will also be presented using Kaplan-Meier estimate and Kaplan-Meier curves (nadir as event and study exit as censor). Table shell's structure is presented in section 19.2.

Table 11-3 – Nadir at follow-up visit by analysis sets and subgroups

	Maniahla		Analysis sets				
VA at Nadir	Variable Type ¹	LEROS ITT	mtDNA subgroups ²	Age at BL subgroups ²	Best VA at BL subgroups ²		
Eyes as base							
Months since BL at Nadir	С	х	х	х	х		
VA by blindness category at Nadir	0	х	х	х	Х		
VA logMAR at Nadir	С	х	Х	Х	Х		

¹ Variable Type: nominal (N), ordinal (O), continuous (C); ² Subgroups are to be analysed as defined in 9.3;

11.2.3 Visual Acuity at follow-up

VA at Month 6, 12, 18 and 24 visits descriptive statistics will be presented both for eyes and patients. Variables to be analysed are presented in Table 11-4. Each follow-up visit will be presented in separate tables. Table shell's structure is presented in section 19.2.

Table 11-4 -Visual Acuity at follow-up visit (Month 6, 12, 18 and 24) by analysis sets and subgroups

		Analysis sets						
VA at Month XX	Variable Type ¹	LEROS mITT/ NH matched sets ²	LEROS ITT	mtDNA subgroups ³	Age at BL subgroups ³	Best VA at BL subgroups ³		
Based in total of Patients				4		***		
Best VA by blindness category	0	Х	х	х	х	Х		
Best VA (logMAR)	С	х	х	X	X	Х		
Change in Best logMAR compared to BL	С	Х	Х	Х	x	Х		
Based in total of Eyes								
Eyes VA by blindness category	0	Х	х	Х	Х	Х		
Eyes VA (logMAR)	С	х	х	х	х	х		
Change in Eyes logMAR compared to BL	С	х	х	х	х	х		

Variable Type: nominal (N), ordinal (O), continuous (C); Matched data sets (as defined in section 8.5) used in the calculation of 12 and 24 months endpoints evaluation; Subgroups are to be analysed as defined in 9.3;

11.3 Concomitant medication/treatment

In CRS-1 and CRS-2 no concomitant medication/treatment information was collected.

The concomitant medication data in LEROS trial will be summarized descriptively for the Safety population. All medications will be classified using the Anatomical Therapeutic Chemical (ATC) classification codes and preferred drug names from the World Health Organization Drug Dictionary (WHO-DD).

Data will be tabulated presenting the number and percentage of patients with receiving at least one medication; patient frequencies and percentages on the ATC Level 1, ATC Level 2, and preferred drug names as exemplified in Table 11-5.

The tables will be sorted by overall descending frequency of ATC Level(s) and then, within an ATC Level, by overall descending frequency of preferred drug name.

Table 11-5 LEROS Concomitant Medication

	n (%)
Number of patients receiving concomitant medication	xx (xx.x%)
ATC Level 1	xx (xx.x%)
- ATC Level 2	xx (xx.x%)
drug name	xx (xx.x%)

11.4 Medical history

LEROS Safety population and CSR-2 patients will be summarized descriptively (separately); and data will be coded using the Medical Dictionary for Regulatory Activities (MedDRA).

The medical history will be tabulated presenting the number and percentage of patients with at least one medical history item; patient frequencies and percentages on the System Organ Class (SOC) and Preferred Term (PT) levels as exemplified in Table 11-6. The table will be sorted by overall descending frequency of SOC and then, within a SOC, by overall descending frequency of PT.

Table 11-6 LEROS and CSR-2 Medical History

	n (%)
Number of patients with at least one medical history term	xx (xx.x%)
SOC	xx (xx.x%)
- PT	xx (xx.x%)

Listings:

CRS-1 data was not collected. It will be provided a listing presenting the investigator's comments at baseline, order by center and patient identification.

SNT-IV-005 Statistical Analysis Plan

Confidential

V1.0 07 June 2021

It will be provided a SOC and PT listing for LEROS Safety population and CSR-2 patients (separately), order by center, patient identification, SOC and PT.

12 Analysis of efficacy

The criteria of inclusion/exclusion for the pre-planned indirect comparison of the primary endpoint against an external natural history control group, where it is only considered who are carriers of only one of the three major LHON mtDNA (G11778A, G3460A or T14484C). Due this criterion, efficacy analysis where there is an indirect comparison to the external natural history control group, will be based on the mITT population.

12.1 Primary endpoint

Endpoint: Proportion of eyes with clinically relevant recovery (CRR) of visual acuity from Baseline (BL) or in which BL VA better than 1.0 logMAR was maintained at Month 12 in patients treated with Raxone® ≤1 year after the onset of symptoms, compared to matching external natural history control group. CRR definition is presented in section 16.

Analysis sets: Primary endpoint analysis will use all LEROS mITT eyes that are ≤1 year since onset of symptoms at BL and have the Month 12 assessment. External NH control set is generated as described in section 8.5.1 (Matching algorithm for the primary endpoint), using VA assessments within 12±3 months from BL.

Analysis method: The primary endpoint will be analysed using a logistic regression model. The binary response will be used as the dependent variable. The independent variables include the treatment group (Raxone® treated patients versus untreated control group), gender (male, female) and mutation group (G11778A, G3460A, T14484C) as fixed factors.

The difference between the Raxone® treated patients versus NH group will be estimated with odds ratio, two-sided 95% confidence intervals and two-sided p-values

```
proc logistic;
  class treatment gender mutation / param=ref;
  model CRB(event='1') = treatment mutation gender / link=logit clodds=pl;
  oddsratio treatment;
run;
```

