9.4.2 Efficacy Evaluation

The primary analysis will be based on Intention-To-Treat principle as change from Baseline.

The primary endpoint will be analysed using a logistic regression model. The binary response will be used as the dependent variable. The independent variables include the treatment group (idebenone treated patients versus untreated control group) and mutation group (G11778A, G3460A, T14484C). The difference between the idebenone treated patients versus untreated control group will be estimated with odds ratio estimates, 95% confidence intervals and two-sided p-values.

All patients who have at least one post-baseline assessment at 12±3 months after Baseline will be included in the primary analysis. This approach is chosen due to the lack of pre-defined visit structure in the control dataset. As a sensitivity analysis, the impact of incomplete data will be assessed by analysing the primary endpoint with a generalized linear mixed model. For this purpose, the SAS GLIMMIX procedure for binomial data with logic link will be used to estimate the treatment differences. Factors similar to the ones used for the primary endpoint will be included in the model. The data from the control dataset will be classified as visits by selecting the assessment which is closest to 6, 12, 18 and 24 months from all assessments conducted within a window of ±3 months. The treatment difference at Month 12 will be estimated using contrasts.

The secondary endpoints based on counts of eyes/patients will be analysed with methods similar to the primary endpoint.

The baseline VA will be used as a covariate and treatment group and mutation as fixed factors. A mixed model for repeated measures (MMRM) will be used to assess the impact of incomplete data. The responder status (CRR or no CRR) will be used as independent variable instead of the treatment group, as this data are not available in the control dataset.

At least the following subgroups will be analysed:

• Each primary LHON mtDNA mutation separately (G11778A, G3460A, T14484C)

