As SNT-CRS-002 study was completed (Clinical Study Report version 1.0 dated 15 July 2019), the data collected in the natural history studies has now been checked for the estimate of the responder rate. Based on the combined data from 175 eyes in the two natural history studies (SNT-IR-006 and SNT-CRS-002), the estimated responder rate is below 22%, i.e. lower than the initially expected rate of 24%. Although the determination of the exact responder rate for the natural history studies requires final data from the LEROS study for matching purposes, it is reasonable to assume that the responder rate of the natural history studies is not higher than 22%. The sample size for LEROS study is therefore re-calculated using the same methods as in the original protocol (Version1.0, 29 January 2016). In order to reach a power of 90% for the comparison of the responder rates between the natural history studies (assumed to be 22% instead of 24%) and the LEROS study (assumed to be 40%, as defined in the protocol), evaluable data from altogether 110 eyes from the LEROS study is required. In order to account for a drop-out rate of 30% (as defined in the protocol), at least 80 patients (equal to 160 eyes) will be enrolled to the LEROS study.

The sample size calculation was done with nQuery Advisor version 8.3.

For the sample size for the eye treated >1 year after the onset of symptoms and the corresponding external natural history control group, the aim is to collect VA data from same number of eyes as for the primary objective in order to compare the patients treated ≤1 and >1 year since the onset of symptoms and to compare patients treated with Raxone >1 year since the onset of symptoms with the corresponding natural history control group, assuming sufficient natural history control data can be collected to generate the natural history control group as described in 8.3.2.

Study: SNT-IV-005

V1.0 07 June 2021

7 Statistical hypotheses

The primary aim of the analysis is to show the superiority of Raxone® (patients treated ≤1 year after onset of symptoms) versus matching NH IDE naïve patients in proportion of eyes with clinically relevant recovery of VA from BL or 12 month maintenance of BL VA better than 1.0 logMAR

H₀: Raxone® (patients treated ≤1 year after onset of symptoms) is not superior to matching NH IDE naïve patients in proportion of eyes with CRR of VA from BL or 12 month maintenance of BL VA better than $1.0 \log MAR$

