8.5.1 Matching algorithm for the primary endpoint

The external NH control set for the eyes with BL \leq 1 year since onset of symptoms in the LEROS ITT population will be generated as follows (section 19.1 presents the matching algorithms using workflow diagrams and provides examples of matched BL and follow-up visits):

1. Since there is no treatment to be considered in the NH control set, in principle any VA observation at any time point after the onset of symptoms in any eye can be used as a BL for that eye. The primary outcome measure in LEROS is the VA at 12 months after BL. Therefore, using a "window" of ±3 months, any eye with a VA observation at any time point in the NH control set which has a follow-up VA assessment within

SNT-IV-005 Statistical Analysis Plan

Confidential

12±3 months will be retained for use as a possible BL observation. All such possible BL observations and subsequent VA assessments will form the NH control subset to be compared to the BL of LEROS.

- 2. In LEROS, the average time from the onset of symptoms to the start of Raxone® treatment will be calculated once all data is available. The start of the Raxone® treatment will be used as the BL in the statistical analyses.
- 3. For each VA observation retained in the NH control subset, the time from the onset of symptoms at each possible BL time point will be calculated for each eye.
- 4. For each eye in the NH control subset, the VA observation for which time since onset of symptoms is closest to the average time since onset of symptoms at BL calculated for LEROS (see 2) will be selected as the BL VA observation for that eye. Any eye in the NH control subset with a BL VA observation >6 months after the average time since onset of symptoms at BL in LEROS will be discarded. The resulting dataset will form the "final NH control subset" to be used for the primary endpoint. In this way, BL observations in the final NH control subset will be closely matched to the BL in the LEROS ITT population.
- 5. The change from BL in VA at 12±3 months for each eye in the final matched NH control subset will be compared to the change from BL visit to the visit scheduled at Month 12 in LEROS.

This algorithm will guarantee that the time from the onset of symptoms to the BL assessment is comparable between the final NH control dataset and LEROS.

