  class treatment gender mutation / param=ref;
  model CRB(event='1') = treatment gender mutation / link=logit clodds=pl;
  ods output ParameterEstimates = ParameterEstimates;
  ods output CLOddsPL = CLOddsPL;
run;
     STEP 5: calculate the logistic analysis combined results*/
proc mianalyze parms(classvar=classval)= ParameterEstimates.;
   modeleffects treatment gender mutation;
run;
```

```
STEP 6: calculate the combined results odds ratio */
/* Transform estimates */
data calculated odds ratio 1;
   label or_value = 'Log odds ratio value'
        or stderr = 'Log odds ratio SE';
  set CLOddsPL;
     or value = log(OddsRatioEst);
     or_stderr= (log(uppercl)-log(lowercl))/(2*1.96);
run;
    Combine transformed estimates */
proc sort data= calculated_odds_ratio_1; by Effect; run;
proc mianalyze data= calculated_odds_ratio_1;
       by Effect;
       modeleffects or_value;
       stderr or_stderr;
       ods output ParameterEstimates = calculated odds_ratio_2;
     run;
     Back-transform combined values */
data calculated odds ratio 3;
   label estimate back = 'Odds ratio'
        lcl back = 'LCL Odds ratio'
        ucl_back = 'UCL Odds ratio';
       set calculated_odds_ratio_2;
       estimate back = exp(estimate); *pooled odds ratio;
       lcl_back=estimate_back*exp(-1.96*stderr); *pooled lower limit;
       ucl_back=estimate_back*exp(+1.96*stderr); *pooled upper limit;
     run;
```

Through inverse probability of treatment

Propensity score will be calculated by means of logistic regression with treatment as dependent variable. Independent variables include gender (male, female), mutation group (G11778A, G3460A, T14484C), age, time since symptoms onset in months and VA at BL (logMAR) as factors.

The same primary model as described above will be applied with the inverse probability weight.

```
SAS code to calculate the propensity score (values: Raxone® treated patients = 1; NH = 0)
proc logistic data=CRB dataset;
  class gender mutation / param=ref;
  model treatment(event='1') = gender mutation age time onset bl va;
  output out=psdataset pred=ps;
run;
data analysis dataset;
  set psdataset;
  if treatment = 1 then ps weight = 1/ps;
  else if treatment = 0 then ps weight = 1/(1 - ps);
run;
SAS code to proceed with the endpoint regression analysis
proc logistic data= analysis dataset;
  class treatment gender mutation / param=ref;
   model CRB(event='1') = treatment gender mutation / link=logit clodds=pl;
  oddsratio treatment;

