  weight ps_weight;
run;
```

Effect of the size of time window used in the matching

The effect of the size of time window used in the matching algorithm can be explored rerunning the algorithm and primary analysis using different time windows

- VA assessments within 12±3.5 months from BL
- VA assessments within 12±4 months from BL

The same primary model as described above will be applied.

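### The primary logistic model treats a patient's two eyes as independent, so the 95% confidence interval that decides superiority is too narrow

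*SAP*

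**What the plan says.** The primary endpoint is a proportion of eyes. SAP 12.1 sets the analysis set on the treated side: "Primary endpoint analysis will use all LEROS mITT eyes that are ≤1 year since onset of symptoms at BL", provided the eye also has a Month 12 assessment. The control side is built the same way in SAP 8.5.1: "For each eye in the NH control subset, the VA observation for which time since onset of symptoms is closest" to the LEROS average is taken as that eye's baseline.

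The model is described as "The primary endpoint will be analysed using a logistic regression model. The binary response will be used as the dependent variable" and coded in PROC LOGISTIC as "model CRB(event='1') = treatment mutation gender / link=logit clodds=pl". Nothing in the text or code identifies the patient.

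Under SAP 7, superiority is declared when the lower limit of the two-sided 95% interval for the odds ratio is above 1. The sample size (SAP 6, protocol 9.6) is also in eyes: "evaluable data from altogether 110 eyes from the LEROS study is required", and 80 patients are equated with 160 eyes.

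The sensitivity analyses reuse the model. For the inverse-probability and time-window runs SAP 12.1.1 says "The same primary model as described above will be applied". The multiple-imputation code there and in SAP 12.4 repeats the same PROC LOGISTIC call and recovers its standard error from the profile-likelihood limits: "or_stderr= (log(uppercl)-log(lowercl))/(2*1.96)". Protocol 9.4.2 offers one other model: "As a sensitivity analysis, the impact of incomplete data will be assessed by analysing the primary endpoint with a generalized linear mixed model".

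**The concern.** Treatment varies only between patients, never between the two eyes of one patient. If fellow eyes tend to share an outcome, two eyes carry less information about treatment than two independent observations. A model that counts them as independent then understates the standard error. The odds ratio is not biased by this, but the interval and p-value are wrong, and an ineffective drug would pass the SAP 7 rule more often than intended.

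Pairing will be common. Protocol 1.1 reports second-eye involvement in over 97% of patients within 12 months.

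No other planned analysis repairs it. The protocol's mixed model is aimed at incomplete data across visits, names no patient effect, and is not carried into SAP 12.1.1. Comparisons of the responder endpoint with controls at patient level, which would avoid the problem, are listed in SAP 12.2 for Months 6, 18 and 24 but not for Month 12.

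The eye-level comparative secondary endpoints inherit the defect. In the >1 year comparison, the selection steps of SAP 8.5.2 and protocol 9.2.2 also let one control eye enter once per onset bin, so up to four times. (The closing note of SAP 8.5.2 describes the bins as follow-up months; the protocol's onset-bin wording fits the selection steps.)

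**Working it through.** **1. The plan's own figure.** Inputs from SAP 6: 40% against 22%, 110 LEROS eyes, 175 natural-history eyes, two-sided 0.05, pooled-variance test, every eye independent.

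- Pooled rate = (44 + 38.5)/285 = 0.2895.
- SE under no difference = √[0.2895 × 0.7105 × (1/110 + 1/175)] = 0.0552.
- SE under the alternative = √[0.40 × 0.60/110 + 0.22 × 0.78/175] = 0.0562.
- Power = Φ[(0.18 − 1.96 × 0.0552)/0.0562] = 89.9%, against the stated 90%.
- Dropout: 110/0.70 rounds up to 158 eyes, or 79 patients, against at least 80.

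The plan's figure is reproduced with no allowance for inter-eye correlation.

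**2. A correlation from the documents.** The EAP table in protocol 1.2 gives CRR by patient and by eye. If a patient counts as a responder when at least one eye responds, then both-eye responders = responding eyes − responding patients. With p the eye-level rate, r = [P(both) − p²]/[p(1 − p)].

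| EAP time | Patients | Responding patients | Responding eyes | Both eyes | p | r (bootstrap 95% interval) |
|---|---|---|---|---|---|---|
| 6 months | 62 | 19 | 30 | 11 | 0.242 | 0.65 (0.38–0.85) |
| 12 months | 47 | 17 | 28 | 11 | 0.298 | 0.70 (0.43–0.90) |
| Last observation | 69 | 34 | 55 | 21 | 0.399 | 0.61 (0.40–0.79) |

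At 12 months independence would predict 47 × 0.298² = 4.2 both-eye responders; there were 11.

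**3. Effect on error rate and power.** Let f1 and f2 be the fractions of treated and control eyes that are paired. The ratio of true to model variance is

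v = [(1 + f1·r)/110 + (1 + f2·r)/175] / (1/110 + 1/175).

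The false-superiority rate is 1 − Φ(1.96/√v), nominally 2.5%. For power, both standard errors in step 1 are multiplied by √v. With all eyes paired, v = 1 + r:

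| r | CI width factor √v | False superiority | Power with a valid interval |
|---|---|---|---|
| 0 | 1.00 | 2.5% | 89.9% |
| 0.2 | 1.10 | 3.7% | 84.1% |
| 0.4 | 1.18 | 4.9% | 78.3% |
| 0.6 | 1.26 | 6.1% | 72.8% |
| 0.7 | 1.30 | 6.6% | 70.3% |

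Two-sided error is twice the third column, so about 7% to 13% for r from 0.2 to 0.7.

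Partial pairing:

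- 80% of eyes paired in both groups: 5.4% at r = 0.6 and 5.8% at 0.7; power 76% and 74%.
- Only treated eyes paired: 3.2% at r = 0.2, 4.7% at 0.6 and 5.1% at 0.7.

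**4. Simulation.** The planned model was run with no treatment effect (22% response, 110 treated and 174 control eyes, 8,000 replicates). With all eyes paired, false superiority was 2.6%, 3.9%, 5.1% and 6.6% at r = 0, 0.2, 0.4 and 0.65. At r = 0.65 the log odds ratio had an empirical SD of 0.406 against a mean model SE of 0.305. A patient-clustered robust variance gave 2.5% to 2.9% throughout. Simulated power with that variance at r = 0.65 was 71%.

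**5. Where it changes the decision.** At the planned rates the unadjusted log odds ratio has SE √(1/44 + 1/66 + 1/38.5 + 1/136.5) = 0.267. The planned rule needs an observed odds ratio above exp(1.96 × 0.267) = 1.69. At r = 0.7 a valid rule needs exp(1.96 × 0.267 × 1.304) = 1.98. Results between these values pass only because of the missing clustering.

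**The case against.** The missing clustering is hard to dispute; the argument is about size and remedy.

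- **The proxy may overstate r.** The EAP figures are recovery from nadir in treated patients. The primary endpoint is recovery or maintained acuity from baseline. Protocol 1.1 says both eyes are usually affected within two to four months, so some patients may enter with one eye near nadir and the other yet to decline. Measuring from baseline keeps that discordance. The EAP correlation is also unadjusted for mutation and gender, which the model includes. Both points stand and are why the range starts at 0.2.
- **Full pairing is an upper bound.** An eye enters only if it is itself within a year of onset and has a Month 12 value, and 175 control eyes is an odd number. This stands; partial-pairing results are shown for that reason.
- **The power reconstruction is not proven.** The nQuery inputs are not stated, and a one-sided 5%, 1:1 calculation gives 112 eyes per group, also close to 110. That calculation likewise treats eyes as independent.
- **The planned effect would still succeed.** At exactly 40% against 22% the odds ratio is 2.36, with a lower limit of 1.40 as planned and 1.20 at r = 0.7. True, but this does not restore the error rate, coverage or power.
- **The comparison is non-randomised.** A clustered variance restores 2.5% only if the groups are otherwise comparable. True, but that is a separate source of error.

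**Conclusion.** The concern holds. The primary analysis as written gives an interval that is too narrow whenever fellow-eye outcomes are positively correlated, and that interval alone decides superiority. Confidence is high on the defect and its direction.

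The size is illustrative. For correlations of 0.2 to 0.7, false superiority is 3.7% to 6.6% with all eyes paired. At 0.6 to 0.7 with partial pairing it is 4.7% to 5.8%. Power with a valid interval is 84% to 70% with all eyes paired, not 90%. These figures assume that EAP recovery from nadir is a usable guide to the upper part of the correlation range, that EAP patient-level response means at least one eye, and that the pairing fractions are as stated; the documents do not give the number of control patients. Patient-level comparisons have no fellow-eye pairing and are not affected.

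**What to change.** Keep the eyes, the endpoint and the covariates; change the variance.

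- **SAP 12.1, 12.1.1, 12.4 and the eye-level endpoints of 12.2:** fit the logistic model by GEE clustered on patient with empirical standard errors, for example PROC GENMOD with `REPEATED SUBJECT=patient / TYPE=EXCH`. `TYPE=IND` is also valid and leaves the planned point estimate unchanged; use it for the inverse-probability-weighted run. Clustering on patient also covers control eyes that re-enter across onset bins.
- **SAP 7:** base the odds ratio interval, p-value and superiority rule on that variance. Remove `clodds=pl`, since GEE has no profile likelihood.
- **Multiple imputation (12.1.1 and 12.4):** pass the GEE log odds ratio and its empirical standard error straight to PROC MIANALYZE rather than back-calculating from profile limits. The imputation code has no fellow-eye or patient term; if its rows are eyes, say how that dependence is preserved.
- **Protocol 9.4.2:** if the mixed model is retained, name a patient random effect.
- **Protocol 9.6 and SAP 6:** restate the power with a stated correlation, pairing fraction and design effect.

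The cost is SAP wording, model code in 12.1, 12.1.1 and 12.4 (12.2 follows by cross-reference), a rewritten pooling step in two places and a revised power paragraph. No new data are needed. The downside is an interval up to about 1.3 times wider (1.27 to 1.30 at correlation 0.6 to 0.7 with all eyes paired, 1.17 to 1.25 with partial pairing) and a lower stated power.
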